| Antiretroviral therapy adherence check, if applicable ^u | X | X | | X | X | | X | X | X | X | X |
| Safety Assessments | | | | | | | | | | | |
| Electrocardiogram | X ^j | | | | | | | | | | |
| Urine pregnancy test ^{k,l} | X | X | | | X | | | | | | |
| Physical examination ^m | X | X | | X | X | | X | X | X | X | X |
| Vital signs ⁿ | X | X | | X | X | | X | X | X | X | X |
| Distribution of subject diary ^o | | X | | | X | | | | | | |
| Completion of diary at home ^p | | X | X | | X | X | | | | | |
| Review of diary by site staff | | | | X | | | X | | | | |
| Adverse events ^q | | Continuous | | | | | | | | | |
| Serious adverse events and immediate reportable events ^r | | Continuous | | | | | | | | | |
| Concomitant medications | X | X | X | X | X | X | X | X | X ^s | X ^s | X ^s |
| Clinical Lab Assessments | | | | | | | | | | | |
| Chemistry (ALT, creatinine) (4 mL) | X | X | | X | X | | X | | | | |
| Hematology ^t (3 mL) | X | X | | X | X | | X | | | | |
| Urinalysis | X | | | | | | | | | | |

| | Screening Phase ^a (≤ 8 weeks) | Vaccination Phase and Post-boost Follow-up ^{b,c} | | | | | | | | | |
|---|---|---|-------|-----|----------------|---------|-----|-----|-----|------|------|
| | | D1 | D2-D7 | D8 | D15 | D16-D21 | D22 | D36 | D57 | D195 | D380 |
| HIV-1 or HIV-1/2 serology (6 mL) | X | | | | | | | | | | |
| CD4+ cell count ^u (4 mL) | X | X | | | X | | | X | X | X | X |
| Immunogenicity and Virologic Assessments ^v | | | | | | | | | | | |
| Blood sampling for humoral assays (16 mL) | | X ^w | | | X ^w | | | X | X | X | X |
| Blood sampling for cellular assays (80 mL) ^d | | X ^w | | | X ^w | | | X | X | X | X |
| HIV viral load quantification and sequencing ^{u,x} (6 mL at screening, 4 mL at other visits) | X | X | | | X | | | X | X | X | X |
| Approximate daily blood draws ^y (mL) | 23 | 111 | 0 | 7 | 111 | 0 | 7 | 104 | 104 | 104 | 104 |
| Approximate cumulative blood draws ^y (mL) | 23 | 134 | 134 | 141 | 252 | 252 | 259 | 363 | 467 | 571 | 675 |

▲ *Ad26.ZEBOV 5x10¹⁰ vp or placebo* ▼ *MVA-BN-Filo 1x10⁸ Inf U or placebo*

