- Up to 20 subjects (10 HIV-infected, 10 healthy) from Part 1 will be asked to enroll for optional apheresis for collection of peripheral blood mononuclear cell (PBMC) and plasma on the Day 36 and Day 57 visit, given that they have provided specific consent for this procedure. Up to a total of 10 Part 1 subjects (irrespective of HIV status) with robust immune responses post-boost may also be enrolled for an optional apheresis procedure performed after unblinding at a predefined visits or at an unscheduled visit for better characterization of immune responses.

- e. Prestudy therapies up to 30 days prior to the start of screening and previous vaccinia/smallpox vaccination at any time prior to study entry must be recorded in the case report form (CRF).
- f. After reading but before signing the informed consent form (ICF), the TOU will be conducted (or as required per local regulations and practice). The ICF needs to be signed before any other study-related activities occur.
- g. The investigators should ensure that all study enrollment criteria have been met at the end of the screening phase. Minimum criteria for the availability of documentation supporting the eligibility criteria are described in Section 17.4.
- h. After each vaccination, subjects will remain at the site for a total of 30 (\pm 10) minutes post-vaccination to monitor for the development of any acute reactions, or longer if deemed necessary by the investigator. Solicited and unsolicited adverse events emerging during the observation period at the site will be recorded in the CRF.
- i. Phlebotomy, indicated pregnancy tests, physical examination and measurements of vital signs will occur prior to study vaccine administration.
- j. Only for subjects >50 years. A single, 12-lead electrocardiogram (ECG) (supine) after at least 5 minutes rest will be performed and interpreted locally. Additional ECG monitoring may be done at other time points during the study if clinically indicated based on signs and symptoms.
- k. Only for women of childbearing potential. A urine pregnancy test should be performed prior to each vaccination administration.
- l. Pregnancies will be reported from signing of the ICF until the end of the study.
- m. A full physical examination, including height and body weight, will be carried out at screening. A genitourinary examination is not required. At other visits, an abbreviated, symptom-directed examination will be performed as indicated by the investigator.

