| Study Vaccine Administration ^{g,h} | | ▲ | | | ▼ | | | | | | |
| | | ▼ | | | ▲ | | | | | | |
| Antiretroviral therapy adherence check, if applicable ^f | X | X | | X | X | | X | X | X | X | X |
| Safety Assessments | | | | | | | | | | | |
| Electrocardiogram | X ^l | | | | | | | | | | |
| Urine pregnancy test ^{l,k} | X | X | | | X | | | | | | |
| Physical examination ^l | X | X | | X | X | | X | X | X | X | X |
| Vital signs ^m | X | X | | X | X | | X | X | X | X | X |
| Distribution of subject diary ⁿ | | X | | | X | | | | | | |
| Completion of subject diary at home ^o | | X | X | | X | X | | | | | |
| Review of diary by site staff | | | | X | | | X | | | | |
| Adverse events ^p | Continuous | | | | | | | | | | |
| Serious adverse events and immediate reportable events ^q | Continuous | | | | | | | | | | |
| Concomitant medications | X | X | X | X | X | X | X | X | X ^r | X ^r | X ^r |
| Clinical Lab assessments | | | | | | | | | | | |
| Chemistry (ALT, Creatinine) (4 mL) | X | X | | X | X | | X | | | | |
| Hematology ^s (3 mL) | X | X | | X | X | | X | | | | |

| | Screening Phase ^a (≤ 8 weeks) | Vaccination Phase and Post-boost Follow-up ^{b,c} | | | | | | | | | |
|--|---|---|-------|-----|----------------|---------|-----|-----|-----|------|------|
| | | D1 | D2-D7 | D8 | D29 | D30-D35 | D36 | D50 | D71 | D209 | D394 |
| Group 1 n=400 | | | | | D15 | D16-D21 | D22 | D36 | D57 | D195 | D380 |
| Group 2 n=100 | | | | | | | | | | | |
| Urinalysis | X | | | | | | | | | | |
| HIV-1 or HIV-1/2 serology (6 mL) | X | | | | | | | | | | |
| CD4+ cell count ^t (4 mL) ^u | X | X | | | X | | | X | X | X | X |
| Immunogenicity and Virologic Assessments ^v | | | | | | | | | | | |
| Mucosal secretions collections (optional) ^w | | X ^x | | | X ^x | | | X | X | X | X |
| Blood sampling for humoral assays (16 mL) | | X ^x | | | X ^x | | | X | X | X | X |
| Blood sampling for cellular assays (80 mL) | | X ^x | | | X ^x | | | X | X | X | X |
| HIV viral load quantification and sequencing ^{ty} (6 mL at screening, 4 mL at other visits) | X | X | | | X | | | X | X | X | X |
| Approximate daily blood draws ^z (mL) | 23 | 111 | 0 | 7 | 111 | 0 | 7 | 104 | 104 | 104 | 104 |
| Approximate cumulative blood draws ^z (mL) | 23 | 134 | 134 | 141 | 252 | 252 | 259 | 363 | 467 | 571 | 675 |

▲ Ad26.ZEBOV 5x10¹⁰ vp or placebo ▼ MVA-BN-Filo 1x10⁸ Inf U or placebo

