- f. The investigators should ensure that all study enrollment criteria have been met at the end of the screening phase. Minimum criteria for the availability of documentation supporting the eligibility criteria are described in Section 17.4.
- g. After each vaccination, subjects will remain at the site for a total of 30 (\pm 10) minutes post-vaccination to monitor for the development of any acute reactions, or longer if deemed necessary by the investigator. Solicited and unsolicited adverse events emerging during the observation period at the site will be recorded in the CRF.
- h. Phlebotomy, indicated pregnancy test, physical examination and measurements of vital signs will occur prior to study vaccine administration.
- i. Only for subjects >50 years. A single, 12-lead ECG (supine) after at least 5 minutes rest will be performed and interpreted locally. Additional ECG monitoring may be done at other time points during the study if clinically indicated based on signs and symptoms.
- j. Only for women of childbearing potential. A urine pregnancy test should be performed prior to each vaccination administration.
- k. Pregnancies will be reported from signing of the ICF until the end of the study.
- l. A full physical examination, including height and body weight, will be carried out at screening. A genitourinary examination is not required. At other visits, an abbreviated, symptom-directed examination will be performed as indicated by the investigator.
- m. Includes blood pressure, pulse/heart rate (at rest) and body temperature (oral or axillary). The site of body temperature measurement must be captured in the CRF.
- n. Diary cards will be used as memory aids to document solicited adverse events by the subject.
- o. Subjects will use the subject diary to document solicited local and systemic adverse events (reactogenicity) in the evening after each vaccination and then daily for the next 7 days at approximately the same time each day. Diaries should be completed at home by the subject. For subjects having difficulty completing the diary independently, the sites will make arrangements to have the diary completed according to their local practice.
- p. Solicitation of any cardiac sign or symptom must be performed at every visit and if indicated, an ECG and/or troponin I levels and/or echocardiogram should be obtained.
- q. For reporting of immediate reportable events, refer to Section 12.3.3.

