Day 380 (365 days Post-dose 2)	[336; 396]	≥ 274	366
Day 394 (365 days Post-dose 2)			

^a The analysis based on the per protocol (PP) analysis set will be restricted to data points that fall within this window (ie, protocol-defined window).

^b The analysis based on the immunogenicity analysis set will be restricted to data points that fall within this window.

Note 1: The analysis windows and target days are based on the relative day (ie, with respect to reference day [day of dose 1 or dose 2 administration]).

Note 2: Day of dose 2 is also considered as Day 1 with respect to the second vaccination (ie, for calculating target days that fall after the second vaccination).

Note 3: Day 36, Day 57, Day 195 and Day 380 apply only to the 14-day interval vaccination schedule. While Day 50, Day 71, Day 209 and Day 394 apply only to the 28-day interval vaccination schedule.

Table 3: Analysis Periods

Phase	Period	Interval	
		From	To
Screening		00:00 on the date of signing the informed consent form	One minute prior to dose 1 administration on Day 1
Regimen*	Post-dose 1	Date and time of dose 1 administration	Minimum of: 
 a) 23:59 on the date of last contact (for early study discontinuation) b) 23:59 on the date of relative Day 29 Post-dose 1 c) 23:59 on planned visit day of dose 2 administration (in case dose 2 is not administered) d) one minute prior to dose 2 administration [□] e) 23:59 on the date of database cut-off (in case of interim analysis)
Post-dose 1 FU		One minute after the end of the Post-dose 1 period	Minimum of: 
 a) 23:59 on the date of last contact (for early study discontinuation or completion) b) one minute prior to dose 2 administration c) 23:59 on the date of database cut-off (in case of interim analysis)
Regimen*	Post-dose 2	Date and time of dose 2 administration	Minimum of: 
 a) 23:59 on the date of last contact (for early study discontinuation or completion) b) 23:59 on the date of relative Day 29 Post-dose 2 c) 23:59 on the date of database cut-off (in case of interim analysis) 
Note: subjects who do not receive dose 2 will not have a Post-dose 2 period.

Post-dose 2 FU		One minute after the end of the Post-dose 2 period	Minimum of: 
 a) 23:59 on the date of database cut-off (in case of interim analysis) b) 23:59 on the date of last contact (for early study discontinuation or completion)

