7.3.1. Definitions

In determining toxicity grades, the following rules will be applied:

- Worst grades/abnormalities are determined over the entire period (eg, Post-dose 1 or Post-dose 2) separately, including all post-baseline measurements of the corresponding period.
- The abnormalities “abnormally low” and “abnormally high” are considered equally important and both abnormalities are shown in the tables. (This means that the sum of the percentages can exceed 100%).
- If a laboratory value falls within the grading as specified in the grading table but also within the local laboratory normal limits, the value is considered as normal or Grade 0.
- Laboratory results falling between the grading scales will be allocated to the adjacent worst-case grade (because the scale for some parameters in the grading table is not continuous as there may be zones where toxicity grade definitions do not exist).

An abnormality (toxicity grade or abnormality based on normal ranges) will be considered as following vaccination in a period and/or phase if it is worse than the corresponding baseline record. If the baseline value is missing, the abnormality is always considered as following vaccination. A shift from “abnormally low” at baseline to “abnormally high” post-baseline (or vice versa) is also considered as an abnormality following vaccination.

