7.3.3. Analysis Methods

Laboratory abnormalities will be determined in accordance with the toxicity grading tables (Attachments 3 and 4), and in accordance with the normal ranges of the clinical laboratory. The worst abnormalities following vaccination will be summarized (ie, showing number and percentage) by vaccination schedule and presented per period/phase, with special attention to Grade 3 toxicities. Focus will be on clinical abnormalities that occur during Post-dose 1 and Post-dose 2 periods, as well as the Regimen period (ie, combined Post-dose 1 and Post-dose 2 periods). Similar tables for worst abnormalities will be provided pooled by vaccine (dose). A listing will also be provided for subjects with clinically significant abnormal laboratory findings.

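### The by-vaccine table of worst laboratory abnormalities takes up to two scheduled draws after dose 1 and one after dose 2, so with unbalanced dose order it can show a vaccine difference that is not there

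*SAP*

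**What the plan says.** SAP 7.3.3 summarizes worst laboratory abnormalities by vaccination schedule and period, then adds: "Similar tables for worst abnormalities will be provided pooled by vaccine (dose"). SAP 7.3.1 defines the worst grade: "Worst grades/abnormalities are determined over the entire period (eg, Post-dose 1 or Post-dose 2) separately, including all post-baseline measurements of the corresponding period". Nothing adjusts for how many measurements a period contains.

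The draws are fixed by the protocol's Time and Events Schedule. In Part 1 the chemistry row reads "Chemistry (ALT, creatinine) (4 mL) | X | X | | X | X | | X", that is screening, Day 1, Day 8, the dose 2 day and 7 days after dose 2. Part 2 has the same pattern ("Chemistry (ALT, Creatinine) (4 mL) | X | X | | X | X | | X"), and the hematology rows match. No safety laboratory draw is scheduled at the 21-day post-boost visit or later. The footnotes put the dose 2 day draw ahead of the injection: "Phlebotomy, indicated pregnancy tests, physical examination and measurements of vital signs will occur prior to study vaccine administration" (Part 1; the Part 2 footnote is equivalent).

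SAP Table 3 ends Post-dose 1 at the earliest of several limits. The two that matter here are "one minute prior to dose 2 administration" and "23:59 on the date of relative Day 29 Post-dose 1". Section 2.1 assigns laboratory abnormalities by these periods and not by time point.

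**The concern.** A maximum over two draws exceeds a threshold more often than a single draw does. A vaccine given mostly as dose 1 therefore collects more opportunities to be called abnormal than one given mostly as dose 2. Dose order is far from balanced in Part 2, so pooling across positions does not even this out.

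The by-vaccine table is the one from which a reader would attribute laboratory abnormalities to one vaccine. There is no formal testing, so the raw percentages are what will be read. Protocol 1.1 already reports decreased neutrophils in 17% of Ad26/placebo and 8% of MVA/placebo subjects after the first dose in a Phase 1 study. An artefact in the same direction could pass for confirmation of that.

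**Working it through.** **Check of the draw schedule.** The documents give no figure for this comparison, but their blood volumes test the schedule. Components: chemistry 4 + hematology 3 = 7 mL; immunogenicity 96 mL; CD4+ count 4 mL and viral load 4 mL in HIV-infected subjects.

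- Screening: 4 + 3 + 6 + 4 + 6 = 23
- Day 1 and dose 2 day: 7 + 96 + 4 + 4 = 111 each
- Day 8 and 7 days post-dose 2: 7 each
- Four later visits: 96 + 4 + 4 = 104 each
- Total: 23 + 111 + 7 + 111 + 7 + 4 × 104 = 675 mL, as stated

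So the later visits contain no safety laboratory volume.

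**Scheduled draws per period.** Post-dose 1: Day 8 and pre-dose 2, so two if dose 2 is given by Day 29. Post-dose 2: the 7-day draw only, so one.

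**Dose order among active subjects (protocol 11.1).** Ad26.ZEBOV first: 320 (Part 2 Group 1). MVA-BN-Filo first: 80 (Part 2 Group 2) and 60 (Part 1).

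**Draws per subject, all Group 1 boosts by Day 29.**

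| Data | Ad26.ZEBOV | MVA-BN-Filo |
|---|---|---|
| Part 2 | (320×2 + 80×1)/400 = 1.80 | (80×2 + 320×1)/400 = 1.20 |
| Parts 1+2 | (320×2 + 140×1)/460 = 1.70 | (140×2 + 320×1)/460 = 1.30 |

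Within each Part 2 cohort (160 and 40) the ratio is again 1.80 to 1.20. In Part 1, and in the pooled 14-day data, there is one sequence only: Ad26.ZEBOV 1, MVA-BN-Filo 2.

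**Expected percentages with no vaccine effect.** Let p be the chance of an abnormality at one draw. The documents give no p; the values below are assumptions. With independent draws, the worst of two is w = 1 − (1 − p)². In Part 2, Ad26.ZEBOV shows 0.8w + 0.2p and MVA-BN-Filo 0.2w + 0.8p.

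| p (assumed) | w | Ad26.ZEBOV | MVA-BN-Filo | Gap (points) |
|---|---|---|---|---|
| 5% | 9.75% | 8.80% | 5.95% | 2.85 |
| 10% | 19.0% | 17.2% | 11.8% | 5.4 |
| 20% | 36.0% | 32.8% | 23.2% | 9.6 |

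Draws from one subject are correlated. With a bivariate normal threshold model at latent correlation 0.5 and p = 10%, w = 16.8%, giving about 15.4% versus 11.4%. With a correlation of 0.6 between the two abnormal/normal indicators, w = 1 − [(0.9)² + 0.6×0.1×0.9] = 13.6%, giving 12.88% versus 10.72%, a gap of 2.2 points.

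If placebo were pooled the same way it would average (2 + 1)/2 = 1.5 draws, or 14.5% at p = 10% with independent draws, matching neither vaccine.

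**Effect of late boosts.** Protocol Table 2 allows the Group 1 boost on Day 29 ± 3 days, and protocol 6.2 allows postponement for acute illness or fever up to 10 days beyond the window. If dose 2 falls after Day 29, the pre-dose 2 draw lands in the Post-dose 1 follow-up phase and no longer counts. Let f be the share of Group 1 boosted after Day 29.

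- Part 2: Ad26.ZEBOV draws = [320(2 − f) + 80]/400; this equals 1.20 at f = 0.75.
- Parts 1+2: [320(2 − f) + 140]/460; this equals 1.30 at f = 180/320 = 0.5625.

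Part 2, p = 10%, independent draws:

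| f | Ad26.ZEBOV | MVA-BN-Filo |
|---|---|---|
| 0 | 17.2% | 11.8% |
| 0.25 | 15.4% | 11.8% |
| 0.50 | 13.6% | 11.8% |
| 0.75 | 11.8% | 11.8% |
| 1 | 10.0% | 11.8% |

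For illustration, boosts spread evenly over Days 26 to 32 give f = 3/7 = 43%, with 14.1% versus 11.8%.

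**After the fix.** One scheduled draw per dose gives p for both vaccines, whatever p, the correlation or f.

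**The case against.** **The phrase is undefined.** The SAP often uses dose for position, so the table could mean vaccine within dose position. Scheduled draws would then be equal between vaccines at each position, apart from the Day 29 limit, and only a dose 1 versus dose 2 reading would be affected. This is possible but the less natural reading. Each sequence here has a single schedule, so such a table would largely repeat the by-schedule, per-period one.

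**Direction and size are not fixed.** This stands. A reader might infer that the plan necessarily overstates Ad26.ZEBOV, or that late boosts reduce the gap without ever removing it. The documents support neither: the Part 2 gap closes at 75% late boosts and reverses beyond that, and no distribution of boost days is given.

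**The rates are assumed, and independence is the extreme case.** Also true, which is why a range is shown.

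**Laboratory results are not the main safety output.** The primary safety endpoints are adverse events, serious adverse events, immediate reportable events and solicited events. Clinically relevant laboratory changes are also recorded as adverse events, and the analysis is descriptive. The main laboratory presentation compares active with placebo within part, cohort and schedule, where scheduled draws are equal. All of this stands and limits the point to one secondary table. In Part 1 and the 14-day pool, pooling by vaccine mixes no dose positions, so the reversed 1-to-2 draw count there is visible from the layout.

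**A footnote on draw counts would do.** It would warn the reader but leave percentages that cannot be compared.

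**Conclusion.** The point holds for the by-vaccine laboratory table. As defined, its percentages mix vaccine with number of draws. At p = 10% and no vaccine effect, the Part 2 gap is 5.4 points with independent draws and about 4 points at latent correlation 0.5, both with every Group 1 boost by Day 29. It falls to zero at 75% late boosts and is −1.8 points (independent draws) if all are late.

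This rests on the pooled reading of the phrase, an assumed per-draw rate and scheduled draws only; unscheduled draws would change the counts. The Parts 1+2 figures are for orientation, because SAP 2.2 pools the two parts only for the 14-day schedule. The by-schedule comparisons of active vaccine with placebo are sound as planned. No error rate is affected. The change should be made because the table invites a comparison between vaccines that its construction cannot support.

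**What to change.** In SAP 7.3.3, state that pooling by vaccine combines dose positions. Base that table on the scheduled 7-day post-dose draw: Day 8 after dose 1, and Day 22 (14-day schedule) or Day 36 (28-day schedule) after dose 2. Use the same draw for any dose 1 versus dose 2 reading. Keep the worst-in-period tables by schedule, with pre-dose 2 and unscheduled results, for active versus placebo.

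The cost is a sentence in the SAP and a filter in the program. The downside is that pre-dose 2 and unscheduled results, including a later-onset or persisting abnormality seen only there, would not appear in the by-vaccine table. They remain available to the by-schedule, per-period tables and the listing.

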7.4. Vital Signs and Physical Examination Findings

Vital sign abnormalities will be determined in accordance with the DMID Vital Signs Toxicity Grading (Attachment 3). The worst abnormalities (following vaccination) of vital signs will be tabulated (ie, showing number and percentage) and listed. Focus will be on the abnormalities that occur during the Post-dose 1 and Post-dose 2 periods, as well as the Regimen period (ie, combined Post-dose 1 and Post-dose 2 periods).

It is important to note that a full physical examination is only conducted at screening. At other visits, only abbreviated, symptom-directed examinations are performed per the investigator's discretion. Therefore, only a listing of subjects with clinically significant physical examination findings (ie, abnormalities) will be provided.

Also, any clinically relevant vital signs or physical examination abnormalities occurring from signing of the ICF onwards until 42-day post dose 2 vaccination are recorded on the AE page of the eCRF and will be analyzed as AE.

7.5. Electrocardiogram

Note that a single, 12-lead electrocardiogram will be performed at screening for subjects >50 years and interpreted locally. Additional ECG monitoring could be done at other time points during the study only if clinically indicated based on signs and symptoms. Therefore, only a listing of subjects with clinically significant electrocardiogram abnormality will be generated.

